5.1 Inclusion Criteria

A subject will be eligible for inclusion in this study only if all of the following criteria apply:

AGE
1. ≥ 21 years of age at the time of signing the informed consent form
TYPE OF SUBJECT AND DIAGNOSIS INCLUDING DISEASE SEVERITY
2. Diagnosis of heart failure (New York Heart Association Class II-IV) for a minimum of 3 months prior to screening
3. Clinically stable with no changes in optimized guidance-directed medications and no hospitalizations for heart failure for at least 1 month prior to Screening
4. NT-proBNP >1000 400 pg/mL measured within 6 months prior to OR at Screening
5. Average DLco measurements outside the normal range (% Predicted DLco < 80%) during the Screening Period
WEIGHT
6. Body mass index (BMI) ≥ 18 and ≤ 40 45 kg/m ²
SEX
7. Male or female of non-childbearing potential

➤ Male patients with female partners of child bearing potential must comply with the following contraception requirements from the time of first dose of study medication until at least five half-lives of study medication OR for a cycle of spermatogenesis following five terminal half-lives after the last dose of study medication.
 
a. Vasectomy with documentation of azoospermia.
 
b. Male condom plus partner use of one of the contraceptive options below:
 
 • Contraceptive subdermal implant that meets the standard operating procedure (SOP) effectiveness criteria including a <1% rate of failure per year, as stated in the product label • Intrauterine device or intrauterine system that meets the SOP effectiveness criteria including a <1% rate of failure per year, as stated in the product label [Hatcher, 2007a] • Oral contraceptive, either combined or progestogen alone [Hatcher,

SEX

2007a]
 
 • Injectable progestogen [Hatcher, 2007a] • Contraceptive vaginal ring [Hatcher, 2007a] • Percutaneous contraceptive patches [Hatcher, 2007a] 
These allowed methods of contraception are only effective when used consistently, correctly and in accordance with the product label. The investigator is responsible for ensuring that subjects understand how to properly use these methods of contraception.
 
➤ A female subject is eligible to participate if at least one of the following conditions applies:
 
 a. Non-reproductive potential defined as: 
 • Pre-menopausal females with one of the following: • Documented tubal ligation • Documented hysteroscopic tubal occlusion procedure with follow-up confirmation of bilateral tubal occlusion • Hysterectomy • Documented bilateral oophorectomy b. Postmenopausal defined as 12 months of spontaneous amenorrhea. Females on hormone replacement therapy (HRT) and whose menopausal status is in doubt will be required to use one of the highly effective contraception methods if they wish to continue their HRT during the study. Otherwise, they must discontinue HRT to allow confirmation of post-menopausal status prior to study enrolment.

INFORMED CONSENT
8. Capable of giving signed informed consent which includes compliance with the requirements and restrictions listed in the consent form and in this protocol

5.2 Exclusion Criteria

A subject will not be eligible for inclusion in this study if any of the following criteria apply:

CONCURRENT CONDITIONS/MEDICAL HISTORY (INCLUDES LIVER FUNCTION AND QTc INTERVAL)

 1. History of acute coronary syndromes including unstable angina or myocardial infarction within 6 months of screening 2. Coronary revascularization including angioplasty and stenting within 6 months of Screening

CONCURRENT CONDITIONS/MEDICAL HISTORY (INCLUDES LIVER FUNCTION AND QTc INTERVAL)

3. History of stroke or seizure disorder within 5 years of Screening
4. Diagnosis of asthma
5. Diagnosis of chronic obstructive pulmonary disease (COPD) with $FEV_1 < 50\%$ of predicted measured within 4 weeks of Screening
6. History of a condition that required radiation therapy to the thorax
7. History of any type of malignancy within the past five years with the exception of successfully treated basal cell cancer of the skin
8. Active ulcer disease or gastrointestinal bleeding at **the time of screening**
9. Current or chronic history of liver disease, known hepatic impairment, or biliary abnormalities (with the exception of Gilbert's syndrome or asymptomatic gallstones)
10. Alanine transaminase (ALT) $> 2 \times$ Upper Limit of Normal (ULN) and bilirubin $> 1.5 \times$ ULN (isolated bilirubin $> 1.5 \times$ ULN is acceptable if bilirubin is fractionated and direct bilirubin $< 35\%$)
11. QTc > 450 msec or QTc > 480 msec in subjects with Bundle Branch Block
 - The QTc is the QT interval corrected for heart rate according to Bazett's formula (QTcB), Fridericia's formula (QTcF), and/or another method, machine-read or manually over-read.
 - The *same* QT correction formula *must* be used for *each individual subject* throughout the study. This formula may not be changed or substituted once the subject has been enrolled.
 - For purposes of data analysis, QTcB, QTcF, another QT correction formula, or a composite of available values of QTc will be used as specified in the Reporting and Analysis Plan (RAP).
12. History or current evidence of any serious or clinically significant gastrointestinal, renal, endocrine, neurologic, hematologic or other condition that is uncontrolled on permitted therapies or that would, in the opinion of the investigator or the GlaxoSmithKline (GSK) medical monitor, make the subject unsuitable for inclusion in this study

CONCOMITANT MEDICATIONS

13. Use of medications specified for the treatment of COPD including short- and long-acting bronchodilators (β -agonists and anticholinergics) and inhaled glucocorticoids as well as oxygen therapy
14. Use of a listed prohibited medication (Section 6.10.2) within the restricted timeframe relative to the first dose of study medication
15. Use of a strong inhibitors or inducers of cytochrome P450 (CYP) 3A or p-

glycoprotein (see Section 6.10.2)

RELEVANT HABITS

16. Current smoker

~~17. History of drug/substance abuse within the past 2 years~~

17. History of alcohol abuse within 6 months of the study **in the opinion of the investigator(s). ~~Defined as an average weekly alcohol consumption of >14 drinks for men or >7 drinks for women. One drink is equivalent to 12 g of alcohol: approximately 12 ounces (360 mL) of beer, 5 ounces (150 mL) of wine, or 1.5 ounces of (45 mL) 80 proof distilled spirits~~**

CONTRAINdications

18. History of sensitivity to any of the study medications, or components thereof or a history of drug or other allergy that, in the opinion of the investigator or Medical Monitor, contraindicates their participation

DIAGNOSTIC ASSESSMENTS AND OTHER CRITERIA

19. Presence of hepatitis B surface antigen (HBsAg), positive hepatitis C antibody test result at screening or within 3 months of screening. For potent immunosuppressive agents, subjects with presence of hepatitis B core antibody (HBcAb) should also be excluded

20. A positive pre-study drug/alcohol screen (**excluding prescribed medications**)

21. Use of another investigational product in a clinical study within the following time period prior to the first administration of study medication in the current study: 30 days, 5 half-lives or twice the duration of the biological effect of the investigational product (whichever is longer)

22. Exposure to more than 4 investigational medicinal products within 12 months prior to the first administration of study medication

PREVIOUS TEXT**5.3 Eligibility for Optional Sleep Apnea Sub-Study**

Subjects eligible for the main study will be eligible for the sleep apnea sub-study, if the following inclusion criterion is met:

REVISED TEXT**5.3 Eligibility for Optional Sleep Apnea Sub-Study**

Subjects eligible for the main study will be eligible for the sleep apnea sub-study, if the following inclusion criterion is met:

Section 6

PREVIOUS TEXT

6.2 Treatment Assignment

Subjects will be assigned to study treatment in accordance with the randomization schedule generated in RandAll NG by Clinical Statistics prior to the start of the study, using validated internal software.

Subjects will be randomized into the study by means of an interactive voice response system (IVRS) i.e. RAMOS NG, to receive one the two treatment regimens shown below in Table 1.

REVISED TEXT

6.2 Treatment Assignment

Subjects will be assigned to study treatment in accordance with the randomization schedule generated in RandAll NG by Clinical Statistics prior to the start of the study, using validated internal software.

Subjects will be randomized into the study by means of an interactive ~~voice web~~ response system (~~IV~~WRS) i.e. RAMOS NG, to receive one the two treatment regimens shown below in Table 1.

PREVIOUS TEXT

6.3 Blinding

This will be a double-blind study where the sponsor and clinical pharmacist are unblinded and the following will apply.

- The investigator or treating physician may unblind a subject's treatment assignment **only in the case of an emergency** OR in the event of a serious medical condition when knowledge of the study treatment is essential for the appropriate clinical management or welfare of the subject as judged by the investigator.
- Investigators have direct access to the subject's individual study treatment.
- It is preferred (but not required) that the investigator first contacts the Medical Monitor or appropriate GSK study personnel to discuss options **before** unblinding the subject's treatment assignment.
- If GSK personnel are not contacted before the unblinding, the investigator must notify GSK as soon as possible after unblinding, but without revealing the treatment assignment of the unblinded subject, unless that information is important for the safety of subjects currently in the study.
- The date and reason for the unblinding must be fully documented in the CRF

- A subject may continue in the study if that subject's treatment assignment is unblinded by the discretion of the Investigator in consultation with the Medical Monitor.
- GSK's Global Clinical Safety and Pharmacovigilance (GCSP) staff may unblind the treatment assignment for any subject with a Serious Adverse Event (SAE). If the SAE requires that an expedited regulatory report be sent to one or more regulatory agencies, a copy of the report, identifying the subject's treatment assignment, may be sent to investigators in accordance with local regulations and/or GSK policy.

REVISED TEXT

6.3 Blinding

This will be a double-blind study where the sponsor and clinical pharmacist are unblinded and the following will apply.

- The investigator or treating physician may unblind a subject's treatment assignment **only in the case of an emergency** OR in the event of a serious medical condition when knowledge of the study treatment is essential for the appropriate clinical management or welfare of the subject as judged by the investigator.
- Investigators have direct access to the subject's individual study treatment **via the IWRS (RAMOS NG).**
- It is preferred (but not required) that the investigator first contacts the Medical Monitor or appropriate GSK study personnel to discuss options **before** unblinding the subject's treatment assignment.
- If GSK personnel are not contacted before the unblinding, the investigator must notify GSK as soon as possible after unblinding, but without revealing the treatment assignment of the unblinded subject, unless that information is important for the safety of subjects currently in the study.
- The date and reason for the unblinding must be fully documented in the CRF
- A subject may continue in the study if that subject's treatment assignment is unblinded by the discretion of the Investigator in consultation with the Medical Monitor.
- GSK's Global Clinical Safety and Pharmacovigilance (GCSP) staff may unblind the treatment assignment for any subject with a Serious Adverse Event (SAE). If the SAE requires that an expedited regulatory report be sent to one or more regulatory agencies, a copy of the report, identifying the subject's treatment assignment, may be sent to investigators in accordance with local regulations and/or GSK policy.

PREVIOUS TEXT

6.7 Treatment of Study Treatment Overdose

GSK does not recommend specific treatment for an overdose. The Investigator (or physician in charge of the subject at the time) will use clinical judgment to treat any overdose.

In the event of an overdose the investigator or treating physician should:

5. Contact the Medical Monitor immediately
6. Closely monitor the subject for adverse events (AEs)/serious adverse events (SAEs) and laboratory abnormalities until GSK2798745 can no longer be detected systemically (at least 5 days for GSK2798745)
7. Obtain a plasma sample for pharmacokinetic (PK) analysis within 1 days from the date of the last dose of study treatment if requested by the Medical Monitor (determined on a case-by-case basis)
8. Document the quantity of the excess dose as well as the duration of the overdosing in the CRF.

Decisions regarding dose interruptions or modifications will be made by the investigator in consultation with the Medical Monitor based on the clinical evaluation of the subject.

REVISED TEXT

6.7 Treatment of Study Treatment Overdose

GSK does not recommend specific treatment for an overdose. The Investigator (or physician in charge of the subject at the time) will use clinical judgment to treat any overdose.

In the event of an overdose the investigator or treating physician should:

1. Contact the Medical Monitor immediately.
2. Closely monitor the subject for adverse events (AEs)/serious adverse events (SAEs) and laboratory abnormalities until GSK2798745 can no longer be detected systemically (at least 5 days for GSK2798745).
3. Obtain a plasma sample for pharmacokinetic (PK) analysis within 1 days from the date of the last dose of study treatment if requested by the Medical Monitor (determined on a case-by-case basis).
4. Document the quantity of the excess dose as well as the duration of the overdosing in the CRF.

Decisions regarding dose interruptions or modifications will be made by the investigator in consultation with the Medical Monitor based on the clinical evaluation of the subject.

PREVIOUS TEXT

6.9.1 Monitoring in the Clinical Research Unit

The first six subjects who participate in the study will be admitted to the Clinical Research Unit to be monitored for the first two days (Day 1 and Day 2) following the first administration of study medication in both study periods. Subsequently, these subjects will remain in the unit for a minimum of 4 hours after the administration of study medication on each of the remaining 5 days (Days 3 through 7) of each study period. On Day 5, subjects will remain in the unit for a minimum of 4 hours after the completion of the saline infusion.

For the remainder of subjects participating in the study, they will remain in the unit for a minimum of 4 hours after the administration of study medication on each of the 7 days of each study period.

Following the completion of all assessments on each study day, subjects may return home. For subjects who cannot return home each evening for multiple reasons including but not limited to distance from clinical site or transportation issues, housing will be provided. All subjects will be continuously monitored remotely (see Section 7.4.7).

REVISED TEXT

6.9.1 Monitoring in the Clinical Research Unit

The first six subjects who participate in the study will be admitted to the **Clinical Research Unit** to be monitored for the first two days (Day 1 and Day 2) following the first administration of study medication in both study periods. Subsequently, these subjects will remain in the unit for a minimum of 4 hours after the administration of study medication on each of the remaining 5 days (Days 3 through 7) of each study period. On Day 5, subjects will remain in the unit for a minimum of 4 hours after the completion of the saline infusion.

For the remainder of subjects participating in the study, they will remain in the unit for a minimum of 4 hours after the administration of study medication on each of the 7 days of each study period.

Following the completion of all assessments on each study day, subjects may return home. For subjects who cannot return home each evening for multiple reasons including but not limited to distance from clinical site or transportation issues, housing will be provided **or they may opt to remain in the unit for the duration of the study period. Housing should be consistent in both study periods.** All subjects will be continuously monitored remotely (see Section 7.4.7).

PREVIOUS TEXT

6.9.2 Meal and Dietary Restrictions

Subjects are not permitted to consume red wine, Seville oranges, grapefruit or grapefruit juice and/or pummelos, exotic citrus fruits, grapefruit hybrids or fruit juices from 7 days prior to the first dose of study medication until their discharge from the unit after their last dose of study medication in each period.

Three meals per day will be provided by dietary department either in the clinical research unit or as a boxed meal(s) to go.

No meal restrictions will be placed with regard to drug administration. Subjects will be allowed to consume a standard breakfast prior to drug administration.

REVISED TEXT

6.9.2 Meal and Dietary Restrictions

Subjects are not permitted to consume red wine, Seville oranges, grapefruit or grapefruit juice and/or pummelos, exotic citrus fruits, grapefruit hybrids or fruit juices from 7 days prior to the first dose of study medication until their discharge from the unit after their last dose of study medication in each period.

Three meals per day will be provided by dietary department either in the ~~clinical research~~ unit or as a boxed meal(s) to go.

No meal restrictions will be placed with regard to drug administration. Subjects will be allowed to consume a standard breakfast prior to drug administration.

PREVIOUS TEXT

6.9.3 Caffeine and Alcohol

During each study period, subjects will abstain from ingesting caffeine- or xanthine-containing products (e.g., coffee, tea, cola drinks, and chocolate) for 24 hours prior to the start of dosing until completion of all assessments.

During each study period, subjects will abstain from alcohol for 24 hours prior to the start of dosing until completion of all assessments.

REVISED TEXT

6.9.3 Caffeine and Alcohol

During each study period, **it is recommended that** subjects will ~~abstain from ingesting minimize ingestion of~~ caffeine- or xanthine-containing products (e.g., coffee, tea, cola drinks, and chocolate) for 24 hours prior to the start of dosing until completion of all assessments.

During each study period, subjects will abstain from alcohol for 24 hours prior to the start of dosing until completion of all assessments.

PREVIOUS TEXT

6.10.2. Prohibited Medications and Non-Drug Therapies

Except for the permitted medications noted above (Section 6.10.1), subjects must abstain from taking non-prescription drugs (including vitamins and dietary or herbal supplements), within 7 days (or 14 days if the drug is a potential enzyme inducer) or 5 half-lives (whichever is longer) prior to the first dose of study medication until completion of the follow-up visit, unless in the opinion of the Investigator and sponsor the medication will not interfere with the study.

Subjects must provide to the investigator information/list of all medications they are currently taking.

GSK2798745 has weak CYP3A4 inhibition potential. There is a likelihood that the concentrations of drugs that are substrates of CYP3A4 may be increased. HMG-CoA reductase inhibitors such as atorvastatin and simvastatin are examples of CYP3A4 substrates that are likely to be taken by the eligible patients as part of their medications. The concentrations of these statins will be monitored during the study. The investigators may also consider substitutions of these medications.

Subjects should avoid using drugs that are strong inhibitors or inducers of Cytochrome P450 (CYP) 3A4 or P-glycoprotein (P-gp) because they may alter GSK2798745 concentrations. The list of background therapy/drugs may be modified based on emerging data. These include, but are not limited to, those listed in Table 2 consider therapeutic substitutions for these medications.

GSK2798745 systemic concentrations will be monitored to detect any drug interactions with moderate CYP3A4 inhibitors or P-gP inhibitors (see SRM for a detailed list).

It is strongly recommended that patients avoid using drugs that are sensitive substrates of Cytochrome P450 (CYP) 3A4 and/or P-gp or that have a low therapeutic index because concentrations of these substrates may be increased by GSK2798745. If co-administration of medications with interaction potential with GSK2798745 is necessary, investigators should monitor subjects for loss of efficacy or consider substitutions of these medications. See SRM for a detailed list. The list may be modified based on emerging data. All concomitant medications should be reviewed by the Medical Monitor and will be to the discretion of the Investigator and Medical Monitor whether the medication can be continued and/or the subject can participate in the study.

REVISED TEXT

6.10.2. Prohibited Medications and Non-Drug Therapies

Except for the permitted medications noted above (Section 6.10.1), subjects must abstain from taking non-prescription drugs (including vitamins and dietary or herbal

supplements), within 7 days (or 14 days if the drug is a potential enzyme inducer) or 5 half-lives (whichever is longer) prior to the first dose of study medication until completion of the follow-up visit, unless in the opinion of the Investigator and sponsor the medication will not interfere with the study.

Subjects must provide to the investigator information/list of all medications they are currently taking.

GSK2798745 has weak CYP3A4 inhibition potential. There is a likelihood that the concentrations of drugs that are substrates of CYP3A4 may be increased. HMG-CoA reductase inhibitors such as atorvastatin and simvastatin are examples of CYP3A4 substrates that are likely to be taken by the eligible patients as part of their medications. The concentrations of these statins will be monitored during the study. The investigators may also consider substitutions of these medications.

Subjects should avoid using drugs that are strong inhibitors or inducers of Cytochrome P450 (CYP) 3A4 or p-glycoprotein (P-gp) because they may alter GSK2798745 concentrations. The list of background therapy/drugs may be modified based on emerging data. These include, but are not limited to, those listed in Table 2 consider therapeutic substitutions for these medications.

GSK2798745 systemic concentrations will be monitored to detect any drug interactions with moderate CYP3A4 inhibitors or P-gP inhibitors (see SRM for a detailed list).

It is strongly recommended that patients avoid using drugs that are sensitive substrates of Cytochrome P450 (CYP) 3A4 and/or P-gp or that have a low therapeutic index because concentrations of these substrates may be increased by GSK2798745. If co-administration of medications with interaction potential with GSK2798745 is necessary, investigators should monitor subjects for loss of efficacy or consider substitutions of these medications. See SRM for a detailed list. The list may be modified based on emerging data. All concomitant medications **should** **may** be reviewed by the Medical Monitor and **it** **will** **be** **up** to the discretion of the Investigator and **if necessary the** Medical Monitor, whether the medication can be continued and/or the subject can participate in the study.

PREVIOUS TEXT

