
 • To determine the effect of GSK2798745 on oxygen saturation • To assess effect of GSK2798745 on sleep-disordered breathing patterns • To determine whether GSK2798745 affects sleep-disordered breathing leading to an 	
 • Change in minimum O₂ saturation measured during polysomnography • Change in apnea-hypopnea index (AHI) determined by polysomnography • Change in the central, obstructive and mixed apnea indexes as determined by polysomnography • Change in respiratory temporal dynamics

[figure not shown]
Objectives	Endpoints

improvement in sympathoadrenal activity
 
 • To determine whether GSK2798745 affects electrocardiographic parameters • To explore the impact of GSK2798745 on the exposure of HMG-CoA reductase inhibitors 	
during in-house sleep apnea evaluation
 
 • Change in plasma and urinary catecholamine concentrations in subjects with sleep-disordered breathing • Changes in time and frequency domain analyses of ECG: HR variability to define sympathetic activity • AUC of HMG-CoA reductase inhibitors and their key metabolites

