6.10.2. Prohibited Medications and Non-Drug Therapies

Except for the permitted medications noted above (Section 6.10.1), subjects must abstain from taking non-prescription drugs (including vitamins and dietary or herbal supplements), within 7 days (or 14 days if the drug is a potential enzyme inducer) or 5 half-lives (whichever is longer) prior to the first dose of study medication until completion of the follow-up visit, unless in the opinion of the Investigator and sponsor the medication will not interfere with the study.

Subjects must provide to the investigator information/list of all medications they are currently taking.

GSK2798745 has weak CYP3A4 inhibition potential. There is a likelihood that the concentrations of drugs that are substrates of CYP3A4 may be increased. HMG-CoA reductase inhibitors such as atorvastatin and simvastatin are examples of CYP3A4 substrates that are likely to be taken by the eligible patients as part of their medications. The concentrations of these statins will be monitored during the study. The investigators may also consider substitutions of these medications.

Subjects should avoid using drugs that are strong inhibitors or inducers of Cytochrome P450 (CYP) 3A4 or p-glycoprotein (P-gp) because they may alter GSK2798745 concentrations. The list of background therapy/drugs may be modified based on emerging data. These include, but are not limited to, those listed in Table 2; consider therapeutic substitutions for these medications.

GSK2798745 systemic concentrations will be monitored to detect any drug interactions with moderate CYP3A4 inhibitors or P-gP inhibitors (see SRM for a detailed list).

It is strongly recommended that patients avoid using drugs that are sensitive substrates of Cytochrome P450 (CYP) 3A4 and/or P-gp or that have a low therapeutic index because concentrations of these substrates may be increased by GSK2798745. If co-administration of medications with interaction potential with GSK2798745 is necessary, investigators should monitor subjects for loss of efficacy or consider substitutions of these medications. See SRM for a detailed list. The list may be modified based on emerging data. All concomitant medications may be reviewed by the Medical Monitor and it will be up to the discretion of the Investigator and if necessary the Medical Monitor, whether the medication can be continued and/or the subject can participate in the study.

Table 2 Strong inducers/inhibitors of CYP3A and P-gp

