9.4.4. Exploratory Analyses

Pharmacokinetic analyses for the statins and any statin metabolites will be the responsibility of the Clinical Pharmacokinetics Modeling & Simulation Department within GlaxoSmithKline. Calculations will be based on the actual sampling times recorded during the study. The systemic concentrations of any HMG-CoA reductase inhibitors (e.g., simvastatin, atorvastatin) and their metabolites will be summarized, as data permit. The details of the PK analysis will be listed in the RAP.

Data from the polysomnography sub-study will be presented in tablular and/or graphical format and summarized descriptively.

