3. SUMMARY OF KEY PROTOCOL INFORMATION

3.1. Changes to the Protocol Defined Statistical Analysis Plan

There were no changes or deviations to the originally planned statistical analysis specified in the protocol amendment 02 (Dated: 19-APR-2016).

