6. GENERAL CONSIDERATIONS FOR DATA ANALYSES AND DATA HANDLING CONVENTIONS

- There are no planned examinations of covariates. The only subgroups analysis planned is by site.
- There are no planned adjustments for multiple comparisons or multiplicity.

[Table 1](#) provides an overview of appendices within the RAP for outlining general considerations for data analyses and data handling conventions.

Table 1 Overview of Appendices

Section	Component
11.1	Appendix 1: Protocol Deviation Definitions for Per Protocol Population
11.2	Appendix 2: Time and Events

Section	Component
11.3	Appendix 3: Treatment States and Phases
11.4	Appendix 4: Data Display Standards & Handling Conventions
11.5	Appendix 5: Derived and Transformed Data
11.6	Appendix 6: Premature Withdrawals & Handling of Missing Data
11.7	Appendix 7: Values of Potential Clinical Importance
11.8	Appendix 8: Laboratory A&R (QUEST: LAB) Dataset Details
11.9	Appendix 9: Biomarker A&R Dataset Details

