11.13.11. Non-ICH Listings

Non-ICH Listings					
No.	Population	IDSL / TST ID / Example Shell	Title	Programming Notes	Deliverable [Priority]
Efficacy					
28	All Subjects	Non-Standard EFF_L1	Listing of Gas Diffusion Outcomes (DLco, DLno, Dm, Vc)		SAC [2]
29	All Subjects	Non-Standard EFF_L2	Listing of Gas Diffusion Outcomes Change from Baseline (DLco, DLno, Dm, Vc)		SAC [2]
30	All Subjects	Non-Standard EFF_L1	Listing of VE/VCO ₂	Rows for day -1 and day 7 only	SAC [2]
31	All Subjects	Non-Standard EFF_L2	Listing of VE/VCO ₂ Change from Baseline	Rows for day -1 and day 7 only	SAC [2]
32	All Subjects	PFT9	Listing of Pulmonary Function Test (FVC, FEV1, FEF-25-75, FEF50, FEF75)	Rows for day -1, day 4, and day 7 only	SAC [2]
33	All Subjects	Non-Standard EFF_L2	Listing of Pulmonary Function Test Change from Baseline (FVC, FEV1, FEF-25-75, FEF50, FEF75)	Rows for day -1, day 4, and day 7 only	SAC [2]
34	All Subjects	LB6	Listing of Troponin	(Include change from baseline)	SAC [2]
35	All Subjects	SF6	Listing of SF-36 Acute Score		SAC [2]
36	All Subjects	MOS_S7	Listing of Sleep Study Variables	Include Minimum Oxygen Saturation during sleep, total sleep time, central apnea index, obstructive apnea index, mixed apnea index, hypopnea index, apnea hypopnea index	SAC[2]

[figure not shown]
Non-ICH Listings					
No.	Population	IDSL / TST ID / Example Shell	Title	Programming Notes	Deliverable [Priority]
40	All Subjects	EFF_L2	Listing of Change in Minimum Oxygen Saturation during Polysomnography		SAC[2]
41	All Subjects	EFF_L1	Listing of AUC of HMG-CoA reductase inhibitors and their key metabolites		SAC[2]
37	All Subjects	SF6	Listing of Dyspnea Score	(Include change from baseline)	SAC[2]
PK					
38	PK	PKCL1P	Listing of Plasma GSK2798745 Pharmacokinetic Concentration-Time Data		SAC [2]
39	PK	PKPL1P	Listing of Derived Plasma GSK2798745 Pharmacokinetic Parameters	Include dose and dose number	SAC [2]

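### The statin-exposure objective reaches the SAP only as a listing: no summary by treatment, no active/placebo AUC ratio, and no declared change from the protocol

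*Protocol*

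**What the plan says.** **Protocol.** Section 3 lists, among the exploratory objectives, "To explore the impact of GSK2798745 on the exposure of HMG-CoA reductase inhibitors", with the endpoint "AUC of HMG-CoA reductase inhibitors and their key metabolites". Section 6.10.2 gives the reason: the drug is a weak CYP3A4 inhibitor, and atorvastatin and simvastatin are substrates that these patients are likely to take. It continues: "The concentrations of these statins will be monitored during the study". Footnote 1 to the Time and Events Table (Section 7.1) assigns statin sampling to some of the study drug's own sampling times, which are the same in each treatment period. On analysis, Section 9.4.4 says: "The systemic concentrations of any HMG-CoA reductase inhibitors (e.g., simvastatin, atorvastatin) and their metabolites will be summarized, as data permit". It leaves the detail to the RAP.

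**SAP.** Section 3.2 repeats the objective and endpoint. The one statin display in Appendix 11 is Listing 41, "Listing of AUC of HMG-CoA reductase inhibitors and their key metabolites", assigned to shell EFF_L1 with no programming note. Tables 4.01 to 4.05 and Figures 4.01 and 4.02 all name GSK2798745 in their titles. Section 3.1 states: "There were no changes or deviations to the originally planned statistical analysis".

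**The concern.** An objective about the impact of a drug on another drug's exposure is a question about a treatment difference. In this design each statin user who completes the study is observed on active and on placebo, with sampling scheduled identically in the two periods. The data can therefore give a within-subject ratio, free of the differences between subjects in statin, dose and exposure level.

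A listing provides neither a summary by treatment nor an estimate with an interval. A reader of the study report would have to judge by eye whether statin exposure rose on active treatment, and two readers could reach different conclusions. Because the SAP declares that nothing changed, the report would also give no sign that a protocol-stated summary had been dropped.

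**Working it through.** The plan states no figure on this point, so the first check is a trace of the objective through the two documents.

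| Step | Protocol | SAP |
|---|---|---|
| Objective | Effect on statin exposure, exploratory (Section 3) | Repeated (Section 3.2) |
| Endpoint | AUC of statins and key metabolites (Section 3) | Repeated (Section 3.2) |
| Sampling | Some of the study-drug times, both periods (Section 7.1, footnote 1) | Same schedule (Appendix 2) |
| Analysis | Descriptive summary where data allow (Section 9.4.4) | No summary table or figure |
| Treatment comparison | Not specified | Not specified |
| Output | Deferred to the RAP | Listing 41 only |
| Departure declared | n/a | None (Section 3.1) |

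SAP Tables 6 and 7 do not name an analyte, so they might be read as covering statins. SAP Section 9.3.1 refers to Appendix 11 for full details, and there every pharmacokinetic table and figure is for GSK2798745. No AUC window for statins is defined anywhere in the SAP. Shell EFF_L1 has columns for sequence, treatment, subject and visit. It has none for statin, statin dose or metabolite, and as drawn it has no Day 1 or Day 7 row, although those are the days with dense sampling.

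The second check is whether a ratio would be informative. The number of statin users and the within-subject CV of statin AUC are not in the documents. The values below are assumptions: 4 or 8 users of one statin, CV 20% or 40%, sequences balanced.

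- Log-scale within-subject SD: s = sqrt(ln(1 + CV²)). CV 20% gives 0.198; CV 40% gives 0.385.
- Multiplicative half-width of the 90% CI in a 2×2 crossover with a period effect: exp(t(0.95, n − 2) × s × sqrt(2/n)).
- n = 4, t = 2.920: CV 20% gives exp(2.920 × 0.198 × 0.707) = 1.51; CV 40% gives exp(2.920 × 0.385 × 0.707) = 2.22.
- n = 8, t = 1.943: CV 20% gives exp(1.943 × 0.198 × 0.5) = 1.21; CV 40% gives exp(1.943 × 0.385 × 0.5) = 1.45.

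For an observed ratio of 1.0, the limits would run from 0.83 to 1.21 in the best of these cases and from 0.45 to 2.22 in the worst. Ignoring the period effect (n − 1 degrees of freedom, t = 2.353) would give 1.90 instead of 2.22 in the worst case, which is too optimistic for this design.

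**The case against.** The strongest reply has four parts.

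- **No contrast was promised.** The objective is exploratory, and Section 9.4.4 offers only a summary, subject to the data. This stands. The ratio is a recommended improvement; only the missing summary is a departure from the protocol.
- **The listing is not empty of information.** AUC is the declared endpoint, and EFF_L1 has a treatment column. Once adapted, Listing 41 would show each user's active and placebo values. This also stands. A reader might infer that the objective is left wholly unanswered, but the values would be visible by treatment, though neither summarized nor estimated.
- **Statin changes can be traced.** Listing 10 covers concomitant medication, entry requires a stable regimen before screening, and significant medication changes are a stopping criterion in Section 5.5.3. So a change between periods would not be hidden. Still, Section 6.10.2 allows substitution of the statin, and Listing 41 has no flag that would tell the reader which pairs of AUCs are comparable.
- **The stakes are limited.** The protocol calls the inhibition weak. SAP Section 2 records that the heart-failure work on this compound will not continue, and statin sampling is done only where possible (Section 7.5.1). This lowers the importance but does not reconcile Section 9.4.4 with SAP Section 3.1.

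A second stronger reading is tempting. Section 6.10.2 also says "GSK2798745 systemic concentrations will be monitored to detect any drug interactions with moderate CYP3A4 inhibitors or P-gP inhibitors", while SAP Section 6 says "The only subgroups analysis planned is by site". A reader might infer that the missing split by inhibitor use is part of the same gap. The documents do not support that. The sentence concerns the opposite direction, other drugs acting on GSK2798745. It is a monitoring statement with no objective, endpoint or analysis attached, so its absence from the SAP does not affect the statin objective.

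**Conclusion.** The point holds in a limited form. The protocol states an exploratory statin-exposure objective and a descriptive summary; the SAP carries the objective forward, replaces the summary with a listing, and declares no change. That mismatch rests on the text alone and needs no assumption. Adding a within-subject active/placebo ratio goes beyond what the protocol promised, but it would turn the objective into an estimate using the sampling already scheduled.

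The precision of that estimate cannot be known from the documents. Under the assumed 4 to 8 users and CV of 20% to 40%, the 90% CI factor is about 1.2 to 2.2. It could exclude a large rise in exposure in the better cases and little in the worst. Splitting users between atorvastatin and simvastatin would reduce the number per ratio and widen the intervals. Nothing here bears on the DLco analysis.

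**What to change.** In SAP Section 9.3 and Appendix 11:

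1. Add a descriptive summary of statin and metabolite exposure by treatment, by statin, with the AUC window defined.
2. For subjects on the same statin and dose in both periods, report each subject's active/placebo AUC ratio over the same sampling window. Where the number of users allows, add the geometric mean ratio with its confidence interval by statin.
3. Flag any subject whose statin or dose changed between periods, and leave that subject out of the ratio. Add columns for statin, dose and metabolite, and rows for the sampled days, to the shell for Listing 41.
4. Correct SAP Section 3.1. It should record the ratio as an addition or, if the summary is not produced, declare that it was dropped and why.

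The cost is SAP wording and one or two small tables. The drawback is wide intervals with few users. If statin samples prove too sparse for an AUC, the SAP should say so and present concentrations at matched times by treatment, which would still meet Section 9.4.4.
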